5.10. Interim Analysis

There are no planned interim analyses. However, safety and erythroid response data will be reviewed periodically throughout the study.

5.11. Protocol Deviations

Protocol deviations will be listed for the following categories:

- Not meeting inclusion/Exclusion criteria
- Withdraw criteria met, but patient not discontinued:
- Failure to perform key procedures
- Study treatment deviation
- Prohibited concomitant medication
- GCP related deviation

5.12. Data Handling

5.12.1. Analysis Visit Window

As specified in [Section 5.1](#), for patients who rollover to Study 06 without interruption, the baseline for Study 04 will be used as the baseline for Study 06; for patients who rollover to Study 06 with interruption, the last value before the first dose of Study 06 will be considered as the baseline. As Study 04 and Study 06 have different schedules of events ([Appendix 3](#) and

[Appendix 4](#)), analysis window will be derived for summary of endpoints by time points. Analysis window determination will be data driven by each parameter. Detailed rules will be specified in the programming specifications.

5.12.2. Handling of Missing Data

As a general principle, no imputation of missing data for other variables will be done. Exceptions are the start and stop dates of AEs and concomitant medication with the rules listed below. The imputed dates will be used to allocate the medication as prior or concomitant medications and to determine whether an AE is/is not treatment emergent. Listings of the AEs and concomitant medications will present the actual partial dates; imputed dates will not be shown.

In addition, partial disease diagnosis dates are imputed to calculate time since disease diagnosis. The listing will present the actual partial dates.

5.12.3. Missing Dates for Adverse Event

- a. Imputing partial AE start dates: If the year is unknown, the date will not be imputed and will be assigned a missing value.
- b. If the month is unknown, then:
 - If the year matches the first dose date, then impute the month and day of the first dose date.
 - Otherwise, assign January.
- c. If the day is unknown, then:
 - If the month and year match the first AE stop month and year and AE stop day is not missing, then impute the start day as the stop day.
 - Otherwise impute start day using the last day of the start month.

Imputing partial AE stop dates:

- a. If the year is unknown, the date will not be imputed and will be assigned a missing value.
- b. If the month is unknown, then assign December.
- c. If the day is unknown, then assign the last day of the month.

5.12.4. Missing Dates for Concomitant Medication

If start date is missing or partial:

- a. if month is missing, use January
- b. if day is missing, use the first day of the month under consideration
- c. if year is missing, use year of the informed consent date
- d. if entire date is missing, use informed consent date

If stop date is missing or partial:

- a. if month is missing, use December
- b. if day is missing, use the last day of the month under consideration

- c. if year or the entire date is missing, set to 31 December 2099

If the imputed start date is after the stop date, then the imputed start date will be one day prior to the stop date.

5.12.5. Missing Dates for Disease Diagnosis Date

For disease diagnosis dates, the imputation rules are

- a. if day is missing, use 15th of the month
- b. if both day and month are missing, impute as January 1st
- c. if month is missing, impute as January
- d. if year is missing, set to missing

5.12.6. Changes in Conduct or Planned Analyses from the Protocol

Major changes between SAP and the planned analysis in Protocol Amendment 4 are described below:

Changes	Rationale
Definition of baseline hemoglobin	Baseline hemoglobin for NTD patients will be the average of two or more measurements performed during the screening period for base study A536-04 (for patients without treatment interruption) or study A536-06 (for patients with treatment interruption). Hemoglobin measurements within 2 weeks following RBC transfusion will be excluded. This definition is revised in this SAP to reflect the derivation rule implemented for this study.
Remove Efficacy Evaluable (EE) population	ITT provides more conservative estimate of treatment effect. Since there is no ITT population, the word mITT was change to ITT to be consistent with study 04 analysis population.

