15. STATISTICS

15.1. Analysis Populations

Analysis Populations:

The modified Intent-to-Treat (mITT) Population: All patients enrolled in the study who received at least one dose of ACE-536.

Efficacy Evaluable (EE) Population: All patients administered at least one dose of ACE-536 and have 1) at least three hemoglobin assessments over an 8-week period, not influenced by transfusion, in NTD patients, OR, 2) at least 8 consecutive weeks of transfusion frequency data in TD patients.

Pharmacokinetics Population: All patients who received at least 1 dose of ACE-536 during Study A536-06 and have sufficient serum ACE-536 values for PK analysis.

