15.2.3. Secondary Analysis

All efficacy analyses will be performed for the EE and mITT populations.

Efficacy will be evaluated by determining the proportion of β -thalassemia patients who have an erythroid response, defined as 1) a mean hemoglobin increase ≥ 1.0 g/dL or ≥ 1.5 g/dL over an 8-week or 12-week period as compared to baseline, not influenced by RBC transfusion in NTD patients or 2) $\geq 20\%$ or $\geq 50\%$ reduction in RBC transfusion burden over an 8-week or 12-week period as compared to the 8-week or 12-week period pretreatment in TD patients.

Baseline hemoglobin for NTD patients will be the average of two or more measurements performed during the screening period for base study A536-04 (for patients without treatment

interruption) or study A536-06 (for patients with treatment interruption). Hemoglobin measurements within 2 weeks following RBC transfusion will be excluded.

Transfusion burden for TD patients will be defined as the ratio of RBC transfusion units (or mLs) transfused during an interval divided by the duration of that interval, where the interval may be during the pretreatment period or the treatment plus follow-up period. The interval during the pretreatment period will be defined as the 8 or 12 weeks prior to Cycle 1 Day 1 of base study A536-04 (will also be analyzed using pretreatment period of study A536-06 for patients with treatment interruption). An interval during the treatment plus follow-up period will be defined as an 8-week or 12-week interval after Cycle 1 Day 1 of study A536-06.

The erythroid response, as defined above, will also be evaluated using other pre-treatment and on-treatment intervals and other % reductions in RBC units transfused, including 100% (transfusion-free).

The erythroid response will be summarized using both a point estimate and its exact 95% CI based on binomial distribution.

No direct comparison testing with concurrent or historical controls will be performed.

Analysis of other secondary efficacy/PD endpoints will include:

- Time to erythroid response and duration of erythroid response
- Change/percent change from pretreatment in mean transfusion burden in TD patients
- Change in mean hemoglobin level in NTD patients
- Change in pre-transfusion hemoglobin levels in TD patients (including analysis of patient subset with < 20% change in transfusion burden)
- Change from baseline in erythropoiesis parameters, including EPO, reticulocytes, nucleated RBCs, and soluble transferrin receptor

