4. ANALYSIS POPULATIONS

4.1. The Intent-To-Treat (ITT) Population

The intent-to-treat (ITT) population consists of all patients enrolled in the study who received at least one dose of ACE-536 in the A536-06 study. This population will be used for all efficacy analysis.

For patients who directly rolled over from A536-04 study, both A536-04 study and A536-06 study data will be included for the analysis.

For interrupted patients, only A536-06 study data will be included for the analysis.

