5.2. General Considerations

Unless otherwise noted, continuous data will be summarized with the following descriptive statistics: number of observations (n), mean, standard deviation (STD), minimum, median, and maximum. Categorical data will be summarized with frequencies (n) and percentages (%). In cases where missing data cause percentages not to sum to 100, a missing data row will be provided. Percentages will use column totals as the denominator unless otherwise indicated. For time to event variables, the Kaplan-Meier curves will be presented if the number of patients is more than 5.

All study data will be included in study data listings. Missing data will generally be treated as missing, not imputed, unless otherwise stated.

Data summaries may also be presented for TD and NTD patients separately as specified. All summaries will be descriptive. No formal hypothesis testing is planned.

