5.7. Efficacy Analyses

No formal hypothesis testing is planned. All efficacy endpoint will be performed using the ITT population.

In general, the below rules apply to the derivations of efficacy endpoints which utilize hemoglobin and RBC transfusion data unless specified otherwise:

- Hemoglobin measurements within 14 days following RBC transfusion will be excluded from the efficacy analysis.
- For each patient, all efficacy endpoints will be derived based on an analysis cutoff day, defined as the last dose + 56 days or the last date from transfusion record data, whichever is earlier.

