5.7.2. Secondary Efficacy Endpoints

5.7.2.1. Erythroid Response

Erythroid response rates will be defined as below for NTD and TD patients.

For NTD patients:

- The proportion of patients with a mean increase of ≥ 1.0 g/dL from pretreatment hemoglobin during any rolling 8 weeks
- The proportion of patients with a mean increase of ≥ 1.5 g/dL from pretreatment hemoglobin during any rolling 8 weeks
- The proportion of patients with a mean increase of ≥ 1.0 g/dL from pretreatment hemoglobin during any rolling 12 weeks
- The proportion of patients with a mean increase of ≥ 1.5 g/dL from pretreatment hemoglobin during any rolling 12 weeks
- The proportion of patients with a mean increase of ≥ 1.0 g/dL from pretreatment hemoglobin during any rolling 24 weeks
- The proportion of patients with a mean increase of ≥ 1.5 g/dL from pretreatment hemoglobin during any rolling 24 weeks
- The proportion of patients with a mean increase of ≥ 1.0 g/dL from pretreatment hemoglobin during weeks 13-24
- The proportion of patients with a mean increase of ≥ 1.5 g/dL from pretreatment hemoglobin during weeks 13-24
- The proportion of patients with a mean increase of ≥ 1.0 g/dL from pretreatment hemoglobin during weeks 37-48

- The proportion of patients with a mean increase of ≥ 1.5 g/dL from pretreatment hemoglobin during weeks 37-48

For TD patients:

- The proportion of patients who have $\geq 20\%$ reduction in RBC transfusion burden compared to pretreatment using rolling 8-week intervals
- The proportion of patients who have $\geq 33\%$ reduction in RBC transfusion burden compared to pretreatment using rolling 8-week intervals
- The proportion of patients who have $\geq 50\%$ reduction in RBC transfusion burden compared to pretreatment using rolling 8-week intervals
- The proportion of patients who have $\geq 20\%$ reduction in RBC transfusion burden compared to pretreatment using rolling 12-week intervals
- The proportion of patients who have $\geq 33\%$ reduction in RBC transfusion burden compared to pretreatment using rolling 12-week intervals
- The proportion of patients who have $\geq 50\%$ reduction in RBC transfusion burden compared to pretreatment using rolling 12-week intervals
- The proportion of patients who have $\geq 33\%$ reduction in RBC transfusion burden compared to pretreatment during weeks 13-24
- The proportion of patients who have $\geq 50\%$ reduction in RBC transfusion burden compared to pretreatment during weeks 13-24

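### An 8-week NTD mean hemoglobin response has no minimum number of readings, so after Cycle 17 it can rest on one or two values

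*SAP*

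**What the plan says.** SAP 5.7.2.1 defines NTD response as a mean rise of at least 1.0 or 1.5 g/dL "from pretreatment hemoglobin during any rolling 8 weeks", with parallel versions for rolling 12 and 24 weeks and for weeks 13-24 and 37-48. It does not say how many readings make a mean. Two general rules bear on window content. SAP 5.7: "Hemoglobin measurements within 14 days following RBC transfusion will be excluded from the efficacy analysis". SAP 5.2: "Missing data will generally be treated as missing, not imputed, unless otherwise stated". No rule says how a patient with too few readings is classified.

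The protocol (15.2.3) planned two efficacy populations: "All efficacy analyses will be performed for the EE and mITT populations". Its mITT population was "All patients enrolled in the study who received at least one dose of ACE-536". Its EE population also asked for "at least three hemoglobin assessments over an 8-week period, not influenced by transfusion, in NTD patients", or 8 consecutive weeks of transfusion data in TD patients. The SAP renames mITT to ITT, says of it in 4.1 "This population will be used for all efficacy analysis", and removes EE in 5.12.6 on the ground that "ITT provides more conservative estimate of treatment effect".

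**The concern.** A mean over few readings is noisier than a mean over many, and response is awarded if any one window in up to 87 cycles qualifies. The sparsest windows are therefore the likeliest to turn chance variation into a response. The 8-week rise of at least 1.5 g/dL is a listed secondary objective (protocol 8.2, SAP 2), reported with an exact confidence interval. That interval reflects binomial sampling only and would not show the inflation. The protocol's own NTD titration rule (10.9.1) looks for a 1.5 g/dL rise sustained over two consecutive measurements, so the documents elsewhere do not treat a single reading as enough.

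**Working it through.** The plan states no sample size, power or error rate, so there is no figure to reproduce. The check has four steps.

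**1. Readings per window.** The schedule of events gives hematology on Day 1 of each 21-day cycle, plus Day 8 of odd cycles up to Cycle 17.

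- Through Cycle 17, a 56-day window holds 3 to 5 scheduled values.
- From Cycle 18, three Day 1 visits span 2 × 21 = 42 days. Of the 21 possible offsets between window start and next visit, 14 (0 to 13 days) fit three visits into 56 days and 7 fit only two. So 7/21, about one third, of fully compliant windows hold two values (34% when counted over the actual schedule).
- With one transfusion on a random day in a late window, the 14-day exclusion leaves one value in about 17-18% of windows and two in about 58-60%.
- An 84-day window holds 6 values early and 4 late.

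**2. One window, no drug effect.** With a baseline from two readings and a window mean from k readings, the chance of exceeding threshold T is 1 − Φ(T / (SD × √(1/k + 1/2))). At an assumed SD of 0.5 g/dL:

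| k | T = 1.5 g/dL | T = 1.0 g/dL |
|---|---|---|
| 1 | 1.5/0.612 = 2.45, 0.72% | 1.0/0.612 = 1.63, 5.1% |
| 2 | 1.5/0.500 = 3.00, 0.14% | 1.0/0.500 = 2.00, 2.3% |
| 3 | 1.5/0.456 = 3.29, 0.05% | 1.0/0.456 = 2.19, 1.4% |

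**3. Any rolling 8-week window over 87 cycles, no drug effect.** Simulation of 4,000 patients per scenario, SD 0.5 g/dL, independent errors, A536-06 schedule:

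| Values missed | Threshold | No minimum | At least 3 in window |
|---|---|---|---|
| 0% | 1.5 g/dL | 4.2% | 1.5% |
| 10% | 1.5 g/dL | 8.1% | 1.4% |
| 30% | 1.5 g/dL | 13.7% | 0.9% |
| 0% | 1.0 g/dL | 33.5% | 20.0% |
| 10% | 1.0 g/dL | 41.5% | 18.5% |
| 30% | 1.0 g/dL | 50.0% | 12.9% |

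Repeated runs at 10% missed agree: about 8% against 1% at 1.5 g/dL, and 42-44% against 17-19% at 1.0 g/dL. Over SD 0.4 to 0.6, the 1.5 g/dL figures run from about 1.5% to 21% with no minimum and from 0.1% to 6% with three values. Confined to the first 17 cycles (SD 0.5, 10% missed), they are only 0.8% against 0.5%, so most of the effect comes from the later 3-weekly schedule. For 1.5 g/dL over 12 weeks, they are 1.0-1.2% against 0.8-0.9%.

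**4. Would EE have prevented this?** EE admits a patient who has three values in one 8-week period anywhere. Every simulated patient met it, so the EE rates equal the no-minimum rates (8.1% and 41.5% at 10% missed). On the 5.12.6 rationale, take 30 NTD patients (assumed), 3 of them outside EE, with 12 responders inside it. EE gives 12/27 = 44.4%. ITT gives 12/30 = 40.0% if the 3 do not respond, and 15/30 = 50.0% only if all 3 do.

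**The case against.** A reader might infer that removing EE stripped out a safeguard on the numerator, and that the SAP's claim of conservatism is therefore wrong. The documents do not support either step. EE decided which patients were analysed, not which windows could count; a patient admitted on three early values could still respond on a later window holding one. The protocol ran the same analyses in mITT, which had no hemoglobin minimum. Few NTD patients would have failed EE in any case: direct roll-overs bring base-study data with roughly weekly hematology (SAP 4.1 and Appendix 3), and interrupted patients have values scheduled on Days 8, 22, 43 and 50. ITT exceeds EE only if patients with sparse data respond more often than the rest.

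Other objections stand in part:

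- The SD and the independence of errors are assumptions. With serially correlated errors the contrast shrinks: one run gave 12.7% against 6.0% at 1.5 g/dL; another, with correlation 0.5 at 3 weeks, gave 50% against 35% at 1.0 g/dL.
- The simulation keeps every patient for 87 cycles and omits the weekly hematology during dose delays and the pre-transfusion readings, all of which affect how many sparse windows occur.
- Much of the rate at 1.0 g/dL remains with three values, because many rolling windows are searched. A minimum count does not cure that.
- Efficacy is secondary and descriptive, and the SAP's 12-week, 24-week and fixed-interval analyses are much less exposed.

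**Conclusion.** The gap is real and confined mainly to the 8-week NTD endpoints: as written, a mean response can rest on one or two readings, and about one third of on-schedule late windows hold only two. With no drug effect, SD 0.5 g/dL, 10% missed and independent errors, this lifts the chance of ever meeting 1.5 g/dL over 8 weeks from about 1% to about 8%. The size depends on the assumed SD, correlation, missingness and time on treatment; the direction was the same in every late-schedule scenario run. The 12-week endpoints hardly move at 10% missed, though heavier missingness would thin those windows too. The gap is common to the protocol and the SAP and should not be put down to the removal of EE. The 5.12.6 rationale is normally correct. This is worth fixing because the rule serves a listed secondary endpoint and the change is cheap, but it does not touch the primary safety objective.

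**What to change.** Keep the ITT denominator. In SAP 5.7.2.1 state that:

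- an 8-week window is evaluable for NTD response only if it holds at least three hemoglobin values not influenced by transfusion;
- a patient with no evaluable window is a non-responder and stays in the denominator.

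The count of three matches the number in the EE definition, but applying it inside the response window is a new rule and should be described as one. In 5.12.6 it is enough to note that ITT is conservative relative to EE only when patients with sparse data do not respond more often. A 12-week minimum is optional, since four values are scheduled even late in treatment.

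The cost is a few sentences of SAP text and programming, with no new data. Reported 8-week response rates become somewhat lower, and about one third of on-schedule windows after Cycle 17 are not evaluable. A sustained responder seen on schedule still qualifies: three consecutive Day 1 visits span 42 days, or 42 + 2 × 5 = 52 days if both intervals use the full 5-day allowance, which fits within 56.

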7. APPENDICES

7.1. Appendix 1 - FACT-An and SF-36 Scoring Algorithm

The Fact-An questionnaire contains 47 questions which are divided into the following sub scales:

- Physical Well-Being (PWB) (7 questions: Item Score range 0 - 28)
- Social/Family Well-Being (SWB) (7 questions: Item Score range 0 - 28)
- Emotional Well-Being (EWB) (6 questions: Item Score range 0 - 24)
- Functional Well-Being (FWB) (7 questions: Item Score range 0 - 28)
- Anemia Subscale (AnS) (20 questions: Item Score range 0 - 80)
- Fatigue Subscale (FACT-F) (13 questions: Item Score range 0 – 52)
- Fatigue Experience (FE) (5 questions: Item Score range 0 – 20)
- Fatigue Impact (FI) (8 questions: Item Score range 0 – 32)

Patients give individual responses to each question on a scale of 0 to 4 (0=Not at all; 1=A little bit; 2=Somewhat; 3=Quite a bit; 4=Very much). Item scores in the PWB and EWB sub scales will be derived by subtracting the response value from 4. Similarly, all Item Scores in the AnS subscale except Item Codes An5, An7, BL4 and An13³ will be derived by subtracting the response value from 4. Thus, a higher Item Scores indicates a better quality of life.

Subscale totals will be derived as follows:

$$\frac{\text{Sum of Item Scores} \times \text{Number of Items in Subscale}}{\text{Number of Items Answered}}$$

For example, if 6 questions are answered in the Physical Well-Being subscale and the Item scores sum to a total score 18 the subscale score will be $(18 \times 7)/6 = 21$.

If 50% or more of responses in any subscale are missing the subscale total will be set to missing.

The following total scores will also be derived:

FACT-An Total Outcome Index (TOI) derived as: PWB + FWB + AnS (Score range 0 – 136)

FACT-G Total Score (FACT-G) derived as: PWB + SWB + EWB + FWB (Score range 0 – 108)

FACT-An Total Score (FACT-An) derived as: PWB + SWB + EWB + FWB + AnS (Score range 0 – 188)

If 20% or more of the responses that contribute to the FACT-G score are missing the FACT-G score will be set to missing (i.e. at least 22 of the 27 items contributing to FACT-G must be present). Furthermore, FACT-An TOI, FACT-G and FACT-An scores should only be calculated if all component subscales have valid scores. If any subscale total is missing the respective total scores to which the subscale contributes will also be set to missing. A higher FACT total score indicates a better quality of life.

SF-36 Scoring Algorithm

The 36 individual items scores will be used to compute the 8 domain scores (Physical Functioning, Role-Physical, Bodily Pain, General Health, Vitality, Social Functioning, Role-Emotional, and Mental Health). The 8 domains scores will be transformed to a scale from 0 to 100. The transformed scores will be used in the analysis. The Physical Component Scores (PCS) and Mental Component Scores (MCS) will be computed from the transformed domain scores.

The scoring of the domain and component scores will follow the following steps:

- Reverse code 10 of the items (Items 1, 6, 7, 8, 9a, 9d, 9e, 9h, 11b and 11d). Algorithm for reverse coding for those 10 items is as follows:

1. If (Item 1 = 1 or 4 or 5) then Item 1 = 6 – Item1,
Else if Item 1 = 2 then Item 1 = 4.4,
Else if Item 1 = 3 then Item 1 = 3.4
2. Item 6 = 6 – Item 6
3. If (Item 7 = 1 or 6) then Item 7 = 7 – Item 7,
Else if Item 7 = 2 then Item 7 = 5.4,
Else if Item 7 = 3 then Item 7 = 4.2,
Else if Item 7 = 4 then Item 7 = 3.1,
Else if Item 7 = 5 then Item 7 = 2.2
4. Reverse scoring of Item 8 depends on whether Item 7 is answered.

If Item 7 is answered, then recode Item 8 as follows:

If pre-coded Item 7 = 1 and Item 8 = 1 then Item 8 = 6, else Item 8 = 6 – Item 8.

If Item 7 is not answered, then recode Item 8 as follows:

1. If Item 8 = 1 then Item 8 = 6,
Else if Item 8 = 2 then Item 8 = 4.75,
Else if Item 8 = 3 then Item 8 = 3.5,
Else if Item 8 = 4 then Item 8 = 2.25,
Else if Item 8 = 5 then Item 8 = 1
2. Item 9a = 6 – Item 9a
3. Item 9d = 6 – Item 9d
4. Item 9e = 6 – Item 9e
5. Item 9h = 6 – Item 9h
6. Item 11b = 6 – Item 11b
7. Item 11d = 6 – Item 11d

- Compute raw scores of each domain by summing up the items in each domain as specified by [Table 2](#). A domain score will be computed only if at least half of the items in the domain are non-missing. If at least half of the items in the domain are non-missing, missing score in the same domain will be replaced by the average value of the non-missing scores. Recoded scores will be used in the summation and the imputation. The raw domain scores will then be transformed into a scale of 0 to 100 based on their lowest and highest value in Table 2, using the following formula:

$$\text{Transformed Score} = ((\text{Actual} - \text{Lowest}) / (\text{Highest} - \text{Lowest})) \times 100$$

Table 2: SF-36 Domain Score Items

Domain	Items	Lowest	Highest
Physical Functioning (PF)	Items 3a, 3b, 3c, 3d, 3e, 3f, 3g, 3h, 3i, 3j	10	30
Role-Physical (RP)	Items 4a, 4b, 4c, 4d	4	20
Bodily Pain (BP)	Items 7 and 8	2	12
General Health (GH)	Items 1, 11a, 11b, 11c, 11d	5	25
Vitality (VT)	Items 9a, 9e, 9g, 9i	4	20
Social Functioning (SF)	Items 6 and 10	2	10
Role-Emotional (RE)	Items 5a, 5b, 5c	3	15
Mental Health (MH)	Items 9b, 9c, 9d, 9f, 9h	5	25

Transformed score will be standardized to z scores based on the following formulas:

$$PF_Z = (PF - 83.29094) / 23.75883$$

$$RP_Z = (RP - 82.50964) / 25.52028$$

$$BP_Z = (BP - 71.32527) / 23.66224$$

$$GH_Z = (GH - 70.84570) / 20.97821$$

$$VT_Z = (VT - 58.31411) / 20.01923$$

$$SF_Z = (SF - 84.30250) / 22.91921$$

$$RE_Z = (RE - 87.39733) / 21.43778$$

$$MH_Z = (MH - 74.98685) / 17.75604$$

Transform z scores to T scores based on the following formulas:

$$PF_T = 50 + PF_Z * 10$$

$$RP_T = 50 + RP_Z * 10$$

$$BP_T = 50 + BP_Z * 10$$

$$GH_T = 50 + GH_Z * 10$$

$$VT_T = 50 + VT_Z * 10$$

$$SF_T = 50 + SF_Z * 10$$

RE_T=50+RE_Z*10

MH_T=50+MH_Z *10

The aggregate physical (AGG_PHYS) and mental (AGG_MENT) component scores are computed as:

$$\begin{aligned} \text{AGG_PHYS} = & (\text{PF_Z} * .42402) + (\text{RP_Z} * .35119) + (\text{BP_Z} * .31754) + \\ & (\text{GH_Z} * .24954) + (\text{VT_Z} * .02877) + (\text{SF_Z} * -.00753) + \\ & (\text{RE_Z} * -.19206) + (\text{MH_Z} * -.22069) \end{aligned}$$

$$\begin{aligned} \text{AGG_MENT} = & (\text{PF_Z} * -.22999) + (\text{RP_Z} * -.12329) + (\text{BP_Z} * -.09731) + \\ & (\text{GH_Z} * -.01571) + (\text{VT_Z} * .23534) + (\text{SF_Z} * .26876) + \\ & (\text{RE_Z} * .43407) + (\text{MH_Z} * .48581) \end{aligned}$$

Physical Component Scores (PCS) and Mental Component Scores (MCS) are computed as:

$$\text{PCS} = 50 + (\text{AGG_PHYS} * 10)$$

$$\text{MCS} = 50 + (\text{AGG_MENT} * 10)$$

